2.3.2 Measurement Times

Subjects will be followed for 4 weeks.

2.3.3 Missing Data

We will first assess the extent and pattern of missing data for all outcomes. If data are missing for only a small proportion, or if the missing is likely to be at random, data analysis will be conducted using available observations.

If a substantial proportion of subjects have missing information, we will further explore the pattern of missing data, and assess whether missingness or loss to follow up is associated with subjects' characteristics, disease severity or any other factors.

2.4 *Statistical Methods*

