5.2.1. Daily Diary

Beginning with the day of enrollment, for 14 consecutive days, subjects will be asked to complete a daily diary. The daily diary is expected to take approximately 10 minutes per day to complete, and will consist of the following 3 sections: 1) FLU-PRO Symptom Questionnaire

("Symptom Diary"); 2) medication adherence, side effect profile (including skin reactions and rash, neuropsychiatric events, nausea, vomiting, and diarrhea), and hospitalization history; and 3) a functional assessment.

Research staff will provide subjects with access to the web-based daily diary. The diary may be completed either by the subject via a secure web-based system that can be accessed from a personal web-enabled device, such as a laptop, personal computer, or tablet; or by personal contact (in-person or telephone) with trained research staff who will ask the questions and complete the web-based survey on behalf of the subject. If the subject is in the hospital, research staff will visit the subject daily to complete the diary.

Each day following enrollment, the research staff will review the subject's previous day's diary to verify whether or not the diary entry was completed. Missed diary entries cannot be made up. If a diary entry is missed, the research staff will call to remind the subject to complete the next diary entry as well as all remaining entries. Research staff may also offer to continue to contact the subject daily to assist the subject in completing the daily diary. If at any point the subject reports a skin reaction, rash, confusion, or hallucinations, research staff will immediately call to instruct the subject to return to the ED for evaluation (see section 7.2).

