8.1.2. Serious Adverse Event

An SAE is an AE that results in one or more of the following outcomes (International Conference on Harmonization (ICH) E6):

- Death during the period of protocol-defined surveillance.
- Events that are life-threatening (i.e., an immediate threat to life).
- Events requiring hospitalization or prolongation of hospitalization.
- Events resulting in a persistent or significant incapacity or substantial disruption of the ability to conduct normal life functions.
- Congenital abnormalities/birth defects.
- Other important medical events that may jeopardize the subject and may require intervention to prevent one of the outcomes listed above.

All SAEs will be recorded on the *SAE Report Form (F21)*, signed by the PI, and followed until satisfactory resolution, or until the event is deemed chronic or the subject is stable.

Many of the subjects enrolled in this study will have significant influenza-related illness, and it is expected that approximately 40% of enrolled subjects will be hospitalized during their enrollment ED visit due to severe influenza at baseline. If the subject is hospitalized due to their baseline illness, the event will not be reported as an SAE. However if the subject's condition worsens after study drug administration and requires prolongation of the hospitalization, the event will be reported as an SAE. Subsequent events that result in hospitalization after the initial ED enrollment visit will be reported as SAEs (see MOP).

Site PIs will report all deaths and immediately life-threatening events to the IRB within 24 hours of awareness. All remaining SAEs will be reported to the IRB within 7 days of awareness, or per institutional policy.

An ISM will be appointed to provide an independent safety review for SAEs immediately after they occur. The ISM will be a clinician with relevant expertise who is not otherwise associated with the study.

A Safety Monitoring Committee (SMC), consisting of the IND sponsor, JHH Co-PIs, Johns Hopkins University Research Program Manager, BARDA Medical Officer, the ISM, and the study biostatistician will review and monitor the safety and compliance data as well as the overall study progress on a regular basis.

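### SAP 2.3.3 accepts plain available-case summaries when data are missing at random, which is not enough for pooled diary means if completion differs by hospital status

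*Combined protocol and SAP*

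**What the plan says.** SAP 2.3.3 has two parts. The first allows analysis of what was observed when little is missing, or, as an alternative, "if the missing is likely to be at random, data analysis will be conducted using available observations". The second applies when a substantial share is missing. The team will then explore the pattern and "assess whether missingness or loss to follow up is associated with subjects' characteristics, disease severity or any other factors". No analysis is named for the case where an association is found, and SAP 2.4.4 excludes modelling.

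The planned diary summaries are unadjusted: FLU-PRO domain means in mock Table 4, a Karnofsky mean in mock Table 5, FLU-PRO over 14 days in Figure 2, and the mean of daily Karnofsky scores in Figure 3. Mock Tables 3 to 5 have columns for site, arm, total and influenza type. None separates admitted from discharged subjects. Table 7 and Figures 4 and 5 cover hospitalised subjects, but only for disease severity and the ordinal scale.

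Protocol 5.2.1 sets the collection rules:
- Duration: "Beginning with the day of enrollment, for 14 consecutive days, subjects will be asked to complete a daily diary".
- In hospital: "If the subject is in the hospital, research staff will visit the subject daily to complete the diary".
- Any subject: web entry, "or by personal contact (in-person or telephone) with trained research staff who will ask the questions".
- After a miss: a reminder call, and "Research staff may also offer to continue to contact the subject daily to assist the subject in completing the daily diary".
- Lost entries: "Missed diary entries cannot be made up".

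Protocol 8.1.2 adds that "it is expected that approximately 40% of enrolled subjects will be hospitalized during their enrollment ED visit due to severe influenza at baseline".

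**The concern.** Missing at random, in the technical sense, lets missingness depend on recorded factors. A raw mean of the observed values is then still biased if such a factor also relates to the score. Hospital status is an obvious candidate. It determines how the diary is collected, and admitted subjects probably differ from discharged ones in symptoms and function.

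If the two groups complete different fractions of their diaries, the pooled mean no longer reflects the enrolled mix. The plan has no step that would correct this and no diary display that would show it. The diary measures are collected to plan endpoints for later trials, so a mis-weighted mean or daily curve would pass into that planning unnoticed.

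**Working it through.** **The plan's own figures.** SAP 2.1 and Protocol 9.2 give 174 eligible and 97 enrolled, of whom 58 are discharged and 39 admitted.
- Eligible: 311 × 0.75 (routine season) × 0.75 (CDC criteria) = 174.9; stated 174.
- Enrolled: 174 × 0.56 = 97.4; stated 97.
- Admitted: 97 × 0.40 = 38.8; stated 39.
- Discharged: 97 × 0.60 = 58.2; stated 58.

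These reproduce. The enrolled admitted share is 39/97 = 40.2%.

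**Assumed inputs, absent from the documents.** Completion while in hospital (cI), completion otherwise (cO), days in hospital (L), and a 20-point Karnofsky gap between admitted and discharged subjects that is constant over the 14 days. I take the Karnofsky score to be the diary's functional assessment.

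**Formulas**, pooling all subject-days:
- Admitted weight w = 39·[L·cI + (14 − L)·cO] / {39·[L·cI + (14 − L)·cO] + 58·14·cO}.
- With L = 14 this reduces to w = 39·cI / (39·cI + 58·cO).
- Shift in the pooled mean = (w − 0.402) × gap. It is zero if completion is equal or if the gap is zero.

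Example with L = 3, cI = 0.95, cO = 0.50: 39 × (2.85 + 5.5) = 325.65 and 58 × 14 × 0.50 = 406, so w = 325.65/731.65 = 44.5%. The shift is (0.445 − 0.402) × 20 = 0.9 points.

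| cI / cO | L (days) | Admitted weight | Weight minus 0.402 | Shift, 20-point gap |
|---|---|---|---|---|
| 95% / 95% | 14 | 40.2% | 0 | 0 |
| 95% / 80% | 3 | 41.2% | +0.010 | 0.2 |
| 95% / 70% | 3 | 42.0% | +0.018 | 0.4 |
| 95% / 50% | 3 | 44.5% | +0.043 | 0.9 |
| 95% / 80% | 14 | 44.4% | +0.042 | 0.8 |
| 95% / 70% | 14 | 47.7% | +0.075 | 1.5 |
| 95% / 50% | 14 | 56.1% | +0.159 | 3.2 |
| 100% / 50% | 14 | 57.4% | +0.171 | 3.4 |
| 70% / 80% | 14 | 37.0% | −0.032 | −0.6 |

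Positive shifts move the pooled mean toward admitted subjects; the last row moves it away.

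**By day.** The 14-day rows also give the weight on any single day when all admitted subjects are still in hospital. Once all have left and completion is equal, the weight returns to 40.2%. A small 14-day average shift can therefore sit almost entirely in the early days of Figures 2 and 3.

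**The case against.** A reader might infer that diary completion depends on hospital status, and that pooled means therefore over-weight sicker inpatients. The documents do not support either step. They show a different mode of collection and state no completion rate. Subjects outside hospital are not left to themselves: staff can complete the diary with them, entries are checked each day, and a miss triggers a call. Protocol 5.1.2 also has the first day's forms done at enrolment. The direction is open too. Subjects who are ventilated, in intensive care or who die may contribute fewer entries than outpatients, and admitted subjects lose the daily visit on discharge. So the effect need not grow over the 14 days.

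The wording can also be read more kindly. The second part of SAP 2.3.3 looks for association with severity, which suggests that the authors meant unrelated to patient factors. On that reading the first part is sound, but the plan still has no analysis for the case where an association appears.

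Other points reduce the effect. Mock Table 3 reports the percentage of diaries completed, and Table 4 counts days missed, though not by disposition. SAP 2.3.1 promises comparisons by clinical characteristics without naming admission. The SAP does not say how Table 4 aggregates over days. Averaging within subject first would largely remove weighting by number of entries, but Figures 2 and 3 would stay exposed. Finally, the trial tests no hypothesis (SAP 2.4.2) and compares no arms (SAP 3.4.1), so no decision rule rests on these means.

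These arguments limit the size, the sign and the priority. They do not make the stated condition sufficient for a raw mean.

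**Conclusion.** The point holds as a fault in the rule and a possible mis-weighting of either sign, not as a demonstrated bias. Missing at random does not by itself justify unadjusted pooled summaries, and SAP 2.3.3 names no follow-up when missingness proves related to severity.

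The size rests wholly on assumed completion rates, days in hospital and score gap. Short stays give an admitted weight of about 41-45% against 40.2%, or 0.2-0.9 Karnofsky points for a 20-point gap. The top of the range, 56-57% and up to about 3.4 points, needs near-complete inpatient diaries for all 14 days and 50% completion outside hospital. Lower completion by inpatients (70% against 80%) gives 37.0%. This is a cheap improvement of low priority.

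**What to change.** In SAP 2.3.3, limit plain available-case summaries to missingness that is small or unrelated to recorded characteristics, and say what follows otherwise:
- Report diary completion and diary means by study day, separately for initially admitted and discharged subjects. Among the admitted, note who is still in hospital that day, because the staff visit follows current status rather than initial disposition.
- Add a combined value standardised to the enrolled admitted and discharged proportions, beside the available-case value. With the planned split, this is 0.402 × admitted mean + 0.598 × discharged mean (58/97 = 0.598).

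Standardising is a weighted average, so SAP 2.4.4 can stand. It works whichever group completes more. It does not correct missingness that depends on the score within a disposition group. Completion by disposition is also a feasibility result in its own right.

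The cost is a wording change, one extra line per diary display, and slightly lower precision when a stratum has few diaries.

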2.4.1 General Overview and Plan of Analysis

The analysis will be performed on data collected from both study sites, JHH and MMC.

2.4.2 Hypothesis Testing

There is no hypothesis testing for the study.

2.4.3 Descriptive Statistics of All Study Variables

Descriptive statistics including mean, median, standard deviation, range for continuous outcomes and frequency/proportion for categorical outcomes will be used to characterize study outcomes.

In addition, we will compare demographic characteristics between those who were enrolled and randomized in the study versus those who were eligible but not enrolled (declined, screen failure, etc.).

2.4.4 Modeling

No statistical modeling will be performed for the study.

2.4.5 Multiple Comparisons

No adjustment for multiple comparisons will be applied.

2.4.6 Project Center Effects

There are two clinical sites in the study. We recommend exploring randomization balance by site. It may also be of interest to compare subject characteristics and the primary outcomes by site.

3. STATISTICAL ANALYSIS

3.1 *Analysis of Subject Characteristics*

Subject characteristics will be presented (see Tables 1 and 2). These characteristics will be summarized separately by study arm as well as combined.

3.2 *Analysis of Primary Objectives*

Primary Objective: To prospectively enroll high-risk subjects with laboratory-confirmed influenza into a randomized, open-label study of oral versus IV influenza therapeutic to include symptom evaluation and outcome assessments.

Analysis: Number of patients screened, enrolled and randomized will be plotted in Figure 1. Descriptive statistics including mean, median, standard deviation, range for continuous outcomes and frequency/proportion for categorical outcomes will be used to characterize study outcomes.

All results will be summarized separately by study arm as well as combined. Results will be summarized in Tables 3-7. Ordinal scale up to 14 days for subjects who initially admitted to the hospital from the emergency department, as well as Karnofsky Performance Scale will also be plotted (Figures 2 and 3).

3.3 *Analysis of Secondary Objectives*

Secondary Objective 1: To identify influenza-positive patients utilizing a previously established triage-based assessment and rapid testing algorithm for suspected influenza infection.

Analysis: Frequencies and proportions will be presented in Table 8.

Secondary Objective 2: To retrospectively evaluate all potentially eligible patients for potential enrollment biases.

Analysis: The analysis will involve a retrospective chart review and comparisons of subject characteristics. It is not part of Westat's scope of work, and is therefore not included in this SAP.

Secondary Objective 3: To create a repository of residual nasopharyngeal (NP) samples collected from ED patients with suspected influenza illness.

Analysis: There is no quantitative data collection for this objective. No statistical analysis will be performed.

3.4 Analysis of Efficacy and Safety

3.4.1 Efficacy

As this is an exploratory study, data analysis will be principally descriptive. Potential clinical endpoints will be described using descriptive statistics for the purposes of future trial planning, and no statistical comparisons between the oral and IV antiviral arms will be made.

3.4.2 Safety

Safety will be assessed by evaluating the clinical significance of laboratory abnormalities and AEs and all serious adverse events SAEs. The overall occurrences of AEs and SAEs will be reported by SOC and PT. The AEs and SAEs will also be evaluated and reported by the relationship to study drug, severity and the outcome. All the results will be summarized by study arm and/or by clinical site as appropriate. Results will be presented in Tables 9 - 11 and Listings 1 – 3.

4. PROPOSED SUMMARY TABLES, GRAPHS AND LISTINGS

4.1 Mock Tables

Table 1. Subject Demographics

Characteristics	Site 1			Site 2			Total		
	Arm 1 (n=)	Arm 2 (n=)	Total (n=)	Arm 1 (n=)	Arm 2 (n=)	Total (n=)	Arm 1 (n=)	Arm 2 (n=)	Total (n=)
Age 65 or Greater									
Chronic Pulmonary									
Chronic Cardiovascular									
Chronic Renal									
Chronic Hepatic									
Chronic Hematologic									
Chronic Metabolic									
Chronic Neurologic									
Immunosuppression									
Pregnancy or Less than Two Weeks Postpartum									
Morbid Obesity									
Resides in Nursing Home									
Native American									

Study Arm:

Arm 1 = Oral antiviral treatment (Oseltamivir)
Arm 2 = IV antiviral treatment (Peramivir)

Table 2. Subject Symptom Onset and Baseline NEWS Score

N (%)	Site 1			Site 2			Total			Influenza Type	
	Arm 1 (n=)	Arm 2 (n=)	Total (n=)	Arm 1 (n=)	Arm 2 (n=)	Total (n=)	Arm 1 (n=)	Arm 2 (n=)	Total (n=)	A (n=)	B (n=)
Time of Symptom Onset at Enrollment											
Within 2 Days											
3 Days											
4 Days											
NEWS Score											
Median (Min—Max)											
0											
1-3											
4-6											
>6											

Table 3. Summary of Subject Status

N (%)	Site 1			Site 2			Total			Influenza Type	
	Arm 1 (n=)	Arm 2 (n=)	Total (n=)	Arm 1 (n=)	Arm 2 (n=)	Total (n=)	Arm 1 (n=)	Arm 2 (n=)	Total (n=)	A (n=)	B (n=)
Subjects Enrolled											
Subjects Completed Treatment (%) in the ED											
Subjects Completed Follow up											
Number of Doses (Median, Min—Max)		-	-		-	-		-	-	-	-
NEWS Score											
Percent Daily Dairies Completed											

Table 4. Summary of FLU-PRO Symptoms

Symptom Severity Score by Domain of Symptoms	Mean (Standard Deviation), Min-Max										
	Site 1			Site 2			Total			Influenza Type	
	Arm 1 (n=)	Arm 2 (n=)	Total (n=)	Arm 1 (n=)	Arm 2 (n=)	Total (n=)	Arm 1 (n=)	Arm 2 (n=)	Total (n=)	A (n=)	B (n=)
Nose											
Throat											
Eyes											
Chest/ Respiratory											
Gastrointestinal											
Body/ Systemic											
Total											
# Days Missed Questionnaire											

Table 5. Clinical Outcomes

Outcomes	Site 1			Site 2			Total			Influenza Type	
	Arm 1 (n=)	Arm 2 (n=)	Total (n=)	Arm 1 (n=)	Arm 2 (n=)	Total (n=)	Arm 1 (n=)	Arm 2 (n=)	Total (n=)	A (n=)	B (n=)
Pneumonia											
Inpatient, n (%)											
Outpatient, n (%)											
Pneumonia Severity Index (Median, Min—Max)											
Hospitalization, n (%)											
LOS (Mean, St. Dev., Min—Max)											
Hospitalization with Pneumonia, n (%)											
LOS (Mean, St. Dev., Min—Max)											
Karnofsky Performance Scale											
Mean, St. Dev.											
Median, Min—Max											
Patient Global Impression of Change (Median, Min—Max)											
Day 7											
Day 28											
Patient Global Impression of Severity (Median, Min—Max)											
Enrollment											
Day 7											
Day 28											

Outcomes	Site 1			Site 2			Total			Influenza Type	
	Arm 1 (n=)	Arm 2 (n=)	Total (n=)	Arm 1 (n=)	Arm 2 (n=)	Total (n=)	Arm 1 (n=)	Arm 2 (n=)	Total (n=)	A (n=)	B (n=)
Number of Subsequent Medical Visits or Hospitalizations (Median, Min—Max)											

Table 6. Influenza-Related Complications

Influenza-Related Complications	# Subjects (%)										
	Site 1			Site 2			Total			Influenza Type	
	Arm 1 (n=)	Arm 2 (n=)	Total (n=)	Arm 1 (n=)	Arm 2 (n=)	Total (n=)	Arm 1 (n=)	Arm 2 (n=)	Total (n=)	A (n=)	B (n=)
Pneumonia											
Myocardial Infarction											
Stroke											
Severity of Disease											
Intensive Care Unit (ICU) Admission											
Mechanical Ventilation											
Oxygen Supplementation											
Ordinal Scale (up to 14 Days)											
Death											
Mechanical Ventilation or Extracorporeal Membrane Oxygenation (ECMO)											
ICU without Mechanical Ventilation or ECMO											
Non-ICU Hospitalization, Requiring Supplemental Oxygen											
Non-ICU Hospitalization, Not Requiring Supplemental Oxygen											
Not Hospitalized, but Unable to Resume Normal Activities											
Not Hospitalized, with Full Resumption of Normal Activities											

Table 7. Characteristics of Subjects Initially Admitted to the Hospital from the ED

Characteristics	# Subjects (%)										
	Site 1			Site 2			Total			Influenza Type	
	Arm 1 (n=)	Arm 2 (n=)	Total (n=)	Arm 1 (n=)	Arm 2 (n=)	Total (n=)	Arm 1 (n=)	Arm 2 (n=)	Total (n=)	A (n=)	B (n=)
Severity of Disease											
Intensive Care Unit (ICU) Admission											
Mechanical Ventilation											
Oxygen Supplementation											
Ordinal Scale (up to 14 Days)											
Death											
Mechanical Ventilation or Extracorporeal Membrane Oxygenation (ECMO)											
ICU without Mechanical Ventilation or ECMO											
Non-ICU Hospitalization, Requiring Supplemental Oxygen											
Non-ICU Hospitalization, Not Requiring Supplemental Oxygen											
Not Hospitalized, but Unable to Resume Normal Activities											
Not Hospitalized, with Full Resumption of Normal Activities											

Table 8. Patient Screening and Testing for Influenza

	Site 1		Site 2		Total	
	N	%	N	%	N	%
Patients through ED						
Of Patients through ED, N(%) Screened with CDG						
Of Patients Screened with CDG, N(%) Who Met Testing Criteria (score ≥ 3)						
Of Patients Who Met Testing Criteria, N(%) Who Had Tests Ordered						
Of Patients Who Met Testing Criteria, N(%) Who Had Tests Collected and Resulted						
Of Those Tested, N(%) Positive for Influenza						
Of Those Tested Positive, N(%) Enrolled and Randomized						

Table 9. Summary of Adverse Events by System Organ Class and Preferred Term, with number (%) of subjects reporting at least one adverse event

SYSTEM ORGAN CLASS	Study Arm 1						Study Arm 2						Total						
	Grade of AE						Grade of AE						Grade of AE						
	Preferred Term	1	2	3	4	5	Total	1	2	3	4	5	Total	1	2	3	4	5	Total

Table 10. Summary of Adverse Events by Relationship to Study Drug and Severity

Adverse Events	Study Arm 1		Study Arm 2		Total	
	# Events	%	# Events	%	# Events	%
Total Number of Adverse Events		-		-		-
Relatedness to Study						
Not related						
Related						
Severity of AE						
Mild						
Moderate						
Severe						
Potentially Life Threatening or Disabling						
Death						

Table 11. Frequency of Protocol-Specific Adverse Event

Symptoms	AE Code (MedDRA, CTCAE)	N (%)
Allergy/Hypersensitivity Reaction		
Rash or Skin Reaction		
Altered Mental Status		

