4.2 Mock Graphs

Figure 1. Study Patient Screening and Enrollment

[figure not shown]

Figure 2. FLU-PRO Symptom Severity Score for Enrolled Patients, by Domain of Symptoms, up to 14 Days from Enrollment

Figure 3. Karnofsky Performance Scale, Mean and 95% Confidence Band of Daily Scores

Figure 4. Severity of Disease for Hospitalized Patients, up to 14 Days from Enrollment

Figure 5. Ordinal Scale for Hospitalized Patients, up to 14 Days from Enrollment

4.3 *Mock Listings*

Listing 1. Patient Level Adverse Events

Patient Identifier	Site	Study Arm	Start Date	Resolution Date	AE Code (MedDRA, CTCAE)	Severity	SAE? (Y/N)	Relatedness	Hospitalization Type	Outcome	Comments

Severity of AE:

- 1 = Mild
- 2 = Moderate
- 3 = Severe
- 4 = Potentially Life threatening or disabling
- 5 = Death

Outcome:

- 1 = Ongoing
- 2 = Resolved without sequelae
- 3 = Resolved with sequelae
- 4 = Death**
- 5 = Worsened
- 6 = Chronic
- 7 = Lost to follow-up

Relatedness to Study Drug:

- 0 = Not related
- 1 = Related

Hospitalization:

- 0 = None
- 1 = ICU
- 2 = Step down unit
- 3 = Other

**Provide further details regarding all reported serious AEs and deaths in the SAE and Subject Deaths tables listed at the end of this section.

Listing 2. Serious Adverse Events

Patient Identifier	Site	Study Arm	SAE Onset Date	Outcome Date	Outcome	SAE Classification	Severity	Related to Study Drug	Description of Actions and Outcomes (e.g. hospitalization, withdrawn from study)

Severity of SAE:

1 = Mild
2 = Moderate
3 = Severe
4 = Life threatening or disabling
5 = Death

SAE Classification:

1 = Death
2 = Life threatening
3 = Inpatient hospitalization or prolonged hospitalization
4 = Persistent/significant disability/incapacity
5 = Resulted in congenital anomaly/birth defect
6 = Important medical event

Relatedness to Intervention:

0 = Not related
1 = Related

Outcome:

1 = Ongoing
2 = Resolved without sequelae
3 = Resolved with sequelae
4 = Death**
5 = Worsened
6 = Chronic
7 = Lost to follow-up

Listing 3. Deaths

Patient Identifier	Site	Study Arm	Age	Date Enrolled	Treatment Date	Cause of Death	Date of Death	Comments

Table of Contents

Sponsor and Principal Investigator Signatures.....	5
List of Abbreviations.....	6
Protocol Summary.....	8
Schematic of Study Design.....	10
1. Background	11
1.1. Scientific Rationale.....	11
1.2. Potential Risks and Benefits.....	11
1.2.1. Potential Risks	12
1.2.2. Potential Benefits.....	14
2. Objectives.....	14
2.1. Study Objectives.....	14

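### No planned summary table gives the per-arm proportion of subjects with a related adverse event; Table 10, the only summary by relatedness, counts events

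*Combined protocol and SAP*

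**What the plan says.** SAP 3.4.2 commits to reporting by relatedness: "The AEs and SAEs will also be evaluated and reported by the relationship to study drug, severity and the outcome". It adds that "All the results will be summarized by study arm and/or by clinical site as appropriate", and says where the results will appear: "Results will be presented in Tables 9 - 11 and Listings 1 – 3". SAP 1.2.2 makes the same commitments on relatedness, arm and site.

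The shells in SAP 4.1 and 4.3 are:

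- **Table 9**: by system organ class and preferred term, "with number (%) of subjects reporting at least one adverse event", split by grade 1 to 5 and by arm. There is no split by relatedness.
- **"Table 10. Summary of Adverse Events by Relationship to Study Drug and Severity"**: relatedness (not related, related) and five severity levels. Each arm has an event-count column and a percentage column. In the first row, "Total Number of Adverse Events", the percentage cell holds a dash. There is no subject count and no arm size.
- **"Table 11. Frequency of Protocol-Specific Adverse Event"**: three event types with a single N (%) column, and no split by arm or relatedness.
- **"Listing 1. Patient Level Adverse Events"**: one line per event, with patient identifier, arm, severity, SAE flag and relatedness coded 0 or 1. Listing 2 carries patient identifier, arm and relatedness for SAEs. Listing 3 (deaths) has no relatedness column.

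**The concern.** For planning a later trial, which is the stated purpose of this pilot, the useful safety quantity is the share of treated subjects in each arm who had at least one event judged related to study drug. The SAP promises reporting by relatedness and by arm, but the only table that does this counts events. An event percentage depends on two things other than how many subjects were affected: how often one subject has repeat events, and how many unrelated events the arm accumulates.

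Both are plausible here. Side effects are asked about in a daily diary for 14 days (Protocol 5.2.1), so one subject can contribute several events. All AEs are recorded whatever their cause (Protocol 8.1.1), and about 40% of subjects are expected to be admitted at the enrollment visit (Protocol 8.1.2), so unrelated illness events can swell the denominator. An AE is presumed related unless another cause is clearly recognized (Protocol 7.1), and a possible relationship counts as related (Protocol 8.1.1), so the related row may well not be empty.

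**Working it through.** **1. Which output carries what.**

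| Output | Unit counted | By arm | By relatedness | Gives a proportion |
|---|---|---|---|---|
| Table 9 | subjects | yes | no | yes |
| Table 10 | events | yes | yes | yes, base unlabelled |
| Table 11 | N (%), unit not stated | no | no | yes |
| Listings 1 and 2 | single events | arm shown per line | shown per line | no |
| Listing 3 | deaths | arm shown per line | no | no |

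No row combines subjects, arm, relatedness and a proportion.

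**2. Arm size for an illustration.** The documents give no AE rates, so event counts must be assumed. Arm size can be taken from the plan. Its enrollment estimate (SAP 2.1, Protocol 9.2) reproduces:

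- Eligible in a routine season: 311 × 0.75 (25% fewer positives) × 0.75 (meeting CDC criteria) = 174.9; the plan states 174.
- Enrolled: 174 × 0.56 = 97.4; the plan states 97.
- Admitted: 97 × 0.40 = 38.8; discharged: 97 × 0.60 = 58.2. The plan states 39 and 58.

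With 1:1 allocation, 97 / 2 = 48.5, so about 49 per arm. The plan's outer figures give 50 / 2 = 25 and 225 / 2 = 112.5, taken as 112.

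**3. One Table 10 entry, many subject risks.** Assume 40 AEs in an arm, 10 of them related. On the likely reading Table 10 prints 10 / 40 = 25%. The 10 related events may lie in one subject or in ten:

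| Subjects in arm | All 10 events in one subject | One event in each of 10 subjects |
|---|---|---|
| 25 | 1/25 = 4.0% | 10/25 = 40.0% |
| 49 | 1/49 = 2.0% | 10/49 = 20.4% |
| 112 | 1/112 = 0.9% | 10/112 = 8.9% |

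**4. One subject risk, many Table 10 entries.** Fix the risk at 10 of 49 subjects (20.4%), with one related event each. With 20, 40 or 80 AEs in total in the arm, the related row reads 10/20 = 50%, 10/40 = 25% or 10/80 = 12.5%.

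**5. If the unlabelled base were subjects.** The dash in the total row fits total events as the base, but this is an inference. With subjects as the base, 10 events over 49 subjects gives 20.4% whether one subject or ten were affected. That is an upper limit on the proportion affected, not the proportion itself.

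**The case against.** The strongest reply is that the information is not lost. SAP 3.4.2 sends results to the listings as well as the tables. Listing 1 has patient identifier, arm and relatedness, and Table 3 gives the number enrolled by arm. A reader might infer that drug-related risk per arm cannot be obtained at all. The documents do not support that: it can be tallied by hand, and only a planned summary is missing. This part of the reply stands and makes the point smaller.

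Other stronger readings also fail:

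- **That severity has the same gap.** Table 9 already plans subject counts by term, grade and arm. The gap is in relatedness.
- **That Table 10 would put the arms in the wrong order.** One can invent such counts: 10 related of 40 events against 5 of 10 gives 25% v 50%, while 10/48 v 5/48 subjects gives 20.8% v 10.4%. But the total event counts are invented, and Table 10 prints the related counts (10 v 5) beside the percentages, in the same order as the subject risks.
- **That correlated events within a subject invalidate the analysis.** This would matter for tests or intervals. SAP 2.4.2 plans no hypothesis tests, SAP 3.4.1 makes no statistical comparison of the arms, and no intervals are planned for AEs.
- **That oversight of subjects is weakened.** Causality is assessed by the site investigator and the independent safety monitor, and SAEs and safety data are reviewed as the study runs (Protocol 8.1.1 and 8.1.2). None of this depends on Table 10.

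It is also fair to say that the shells are headed as proposed and that the text of 3.4.2 fixes no counting unit. That makes the change easy, but leaves the gap in the outputs as drawn. The descriptive nature of the pilot does not remove it either, because the plan itself promises summaries by relatedness and by arm.

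**Conclusion.** The point holds in a limited form. Table 10 is the only planned summary by relatedness. It counts events, and its percentage has no labelled base. The per-arm proportion of subjects with at least one related AE is in no summary table, although the data for it will be collected and listed.

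The size of the gap can only be illustrated. With 10 related of 40 events, both assumed, and 49 subjects in the arm, the same printed 25% is compatible with 2.0% to 20.4% of subjects affected. The absence of the subject-level figure follows from the shells and needs no assumption. Reading the percentage as percent of events is an inference, but the conclusion is the same if the base is subjects.

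This is a minor improvement to descriptive safety reporting. It has no bearing on the primary feasibility objective.

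**What to change.** Add `# Subjects (%)` columns for each arm and for the total to Table 10. The SAP already uses that format in Tables 6 and 7. Count each subject once for any AE, once for any related AE and once for any SAE; a row for each subject's highest grade is optional.

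State the denominator as the number of subjects in the arm who received study drug, and print it in the column head. This needs a sentence of its own: SAP 2.2 defines no treated population, and Protocol 10.2 foresees subjects who receive none of the assigned treatment.

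Keep the event counts and label the base of their percentage, for example as percent of all AEs in the arm.

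The cost is a few extra columns and one stated denominator. No new data are needed, since Listing 1 already carries relatedness, arm and patient identifier. No testing or comparison between arms is implied.
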